9.5.3 Statistical Methodology for Secondary and Other Efficacy Analysis

Secondary and exploratory endpoints that are measurement variables will use similar statistical methodology to the methodology used for primary analysis. Efficacy variables that are proportions will be analyzed using Mantel-Haenszel test, controlling for Stratum, if appropriate. For the analysis of the categories for responders, a Cochran-Mantel-Haenszel test will be used.

Methodologies for variables that are proportions will include construction of confidence intervals for each treatment group and for the difference between groups. For analysis, Fisher's exact test will be used for single-population analysis, and a Mantel-Haenszel test will be used for analyses combining data across strata.

Methodologies for time-to-event variables will include construction of 95% confidence intervals for each group separately and for the difference between groups. For analysis, a Wilcoxon test will be used for single-population analysis, and a van Elteren test will be used for analyses combining data across strata.

Subgroup analyses will be done as identified in the SAP.

Responders based on the ADAS-cog total score, will be assessed using cumulative percentage plots. Similarly, responders based on the CDR-sb score will be assessed using cumulative percentage plots. The y-axis will show the cumulative percentage of patients who achieved the specific measure of improvement in the ADAS-cog (or CDR-sb) total score shown on the x-axis with a separate cumulative percentage curve for each treatment group.

Time to loss of one global stage on the global CDR will include Kaplan-Meier curves. Survival estimates for treatment groups will be compared using the logrank statistic. Observations will be treated as right censored for participants who complete the study without a loss of one stage on the global CDR score or who discontinue the study prematurely.

The proportion of participants who experience loss of one global stage on the CDR will be assessed at each Visit using logistic regression with treatment (as a categorical/class variable), Baseline CDR global score (as a continuous variable).

Summary measures from the analysis will include the odds ratio, 95% confidence interval for the odds ratio, and p-value for treatment comparison. Additionally, the proportion of participants in each CDR global stage will be presented.

For change from Baseline in plasma concentrations of A β species, an MMRM analysis similar to that described for the co-primary endpoints with baseline plasma concentrations of A β species as a continuous covariate will be performed.

For change from Baseline in NPI and MMSE, an MMRM analysis similar to that described for the co-primary endpoints with baseline NPI, and MMSE, as a continuous covariate, respectively, will be performed.

Individual item responses on the RUD Lite questionnaire and the total caregiver/informant time spent assisting the patient based on the RUD Lite questionnaire will be summarized by treatment group.

For change from baseline in DEMQOL-Proxy total score, an ANCOVA analysis with Baseline DEMQOL-Proxy as a continuous covariate will be performed.

If the distribution of any of the above parameters, key secondary, or other secondary endpoints does not appear to be normally distributed, the rank analogues will be utilized.

9.5.4 Subgroup Analyses

Subgroup analyses will be based on the study as a whole. Subgroup analysis will include examination of consistency of efficacy results (ADAS-cog and CDR-sb) over subsets determined by demographic and baseline characteristics. The SAP will include details for subgroup analysis.

9.5.5 Adjustment for Multiple Comparisons

Multiplicity of the primary efficacy analyses is controlled by using a conditional sequence of hypotheses. The study will be considered to demonstrate statistical significance if the primary analysis has a resulting p-value less than 0.05. No other adjustment for multiplicity is required.

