9.0 DATA ANALYSIS/STATISTICAL METHODS

The statistical considerations summarized in the following subsection outline the plan for data analysis of this study. A final and complete Statistical Analysis Plan (SAP) will be finalized prior to unblinding the data from the study. The SAP will supersede the protocol. Any deviations from the planned analyses will be described and justified in the final integrated study report.

This trial describes two studies with a common infrastructure in a single protocol. Statistical analysis of the clinical efficacy variables will be done for each of the studies separately. Statistical analysis of safety and imaging data will be done for the study as a whole (combined).

Continuous variables will be presented showing number of observations available, mean, median, minimum, maximum, 1st and 3rd quartiles, and standard deviations (or standard errors, depending on the variable) by visit. Categorical variables will be presented showing frequencies and percentages by visit.

All tests will be 2-sided and use an overall study-wise $\alpha = 0.05$ unless otherwise stated. SAS Version 9.1 or later will be used. Medical dictionary for Regulatory Activities.

(MedDRA) Version 16.0 or later will be used for coding adverse events. Medications will be coded using WHO Drug Dictionary (WHODD) Version March 2009 or later.

This study is planned using an enrichment strategy, following the draft regulatory guidance depicted in the FDA guidance *Enrichment Strategies for Clinical Trials to Support Approval of Human Drugs and Biological Products* (draft guidance, December, 2012). This study features a conditional sequential approach to hypothesis testing to control alpha, similar to methods using Bauer closed procedures, which are referenced in the FDA adaptive design guidance FDA guidance *Adaptive Design for Clinical Trials for Drugs and Biologics* (draft guidance, February 2010) referenced above), and principles for subgroup analyses.

This study comprises two independent sub-studies in one main study for purposes of independent replication for the co-primary variables: A-Study is composed of the first approximately 400 patients randomized; B-Study is composed of the remaining approximately 400 patients randomized. The study as a whole will be analyzed for specified inferential purposes. A-Study and B-Study will be randomized separately.

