9.2 STATISTICAL HYPOTHESES

A 2-stage conditional sequence of statistical hypothesis tests, will be used. The testing sequence will be as follows:

- Stage 1: 4 concurrent analyses will be done:
 - A-study analysis of co-primary variables:
 - ADAS-cog is analyzed in A-Study.
 - CDR-sb is analyzed in A-Study
 - B-study analysis of co-primary variables:
 - ADAS-cog is analyzed in B-study.
 - CDR-sb is analyzed in B-study

- Stage 2: Conditional on statistical significance of both A-study and B-study in both co- primary variables, testing will continue:
 - MRI assessment is analyzed in the study (as a whole).

For simplicity in notation, thresholds for significance are indicated as “ $p < 0.05$ ”; however, “0.05” is representative of the alpha allocated to the analysis. The overall study-wise alpha is 0.05, but particular analyses may have alpha less than 0.05.
STAGE 1:

Hypothesis tests for A-study are as follows:

The first set of hypotheses to be tested is as follows:

- $H_{01}: \mu(\text{ADAS-cog, azeliragon, A-study}) = \mu(\text{ADAS-cog, P, A-study})$
- $H_{11}: \mu(\text{ADAS-cog, azeliragon, A-study}) \neq \mu(\text{ADAS-cog, P, A-study}),$

where $\mu(\text{ADAS-cog, azeliragon, A-study})$ and $\mu(\text{ADAS-cog, P, A-study})$ denote the true mean changes from Baseline at Month 18 on the ADAS-cog total score for the A-study azeliragon 5 mg/day added to SoC and placebo added to SoC groups, respectively.

The second set of hypotheses to be tested is as follows:

- $H_{02}: \mu(\text{CDR-sb, azeliragon, A-study}) = \mu(\text{CDR-sb, P, A-study})$
- $H_{12}: \mu(\text{CDR-sb, azeliragon, A-study}) \neq \mu(\text{CDR-sb, P, A-study}).$

where $\mu(\text{CDR-sb, azeliragon, A-study})$ and $\mu(\text{CDR-sb, P, A-study})$ denote the true mean changes from Baseline at Month 18 on the CDR-sb score for the A-study AD azeliragon 5 mg/day and placebo groups, respectively.

Hypothesis tests for B-study are as follows:

The first set of hypotheses to be tested in B-study (the third set of hypotheses for the study as a whole) is as follows:

- $H_{03}: \mu^{(\text{ADAS-cog, azeliragon, B-study})} = \mu^{(\text{ADAS-cog, P, B-study})}$
- $H_{13}: \mu^{(\text{ADAS-cog, azeliragon, B-study})} \neq \mu^{(\text{ADAS-cog, P, B-study})}$,

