where $\mu^{(\text{ADAS-cog, azeliragon, B-study})}$ and $\mu^{(\text{ADAS-cog, P, B-study})}$ denote the true mean changes from Baseline at Month 18 on the ADAS-cog total score for the B-study azeliragon 5 mg/day added to SoC and placebo added to SoC groups, respectively.

The second set of hypotheses to be tested in B-study (the fourth set of hypotheses for the study as a whole) is as follows:

- $H_{04}: \mu^{(\text{CDR-sb, azeliragon, B-study})} = \mu^{(\text{CDR-sb, P, B-study})}$
- $H_{14}: \mu^{(\text{CDR-sb, azeliragon, B-study})} \neq \mu^{(\text{CDR-sb, P, B-study})}$.

where $\mu^{(\text{CDR-sb, azeliragon, B-study})}$ and $\mu^{(\text{CDR-sb, P, B-study})}$ denote the true mean changes from Baseline at Month 18 on the CDR-sb score for the B-study AD azeliragon 5 mg/day and placebo groups, respectively.

STAGE 2:

If and only if both hypothesis tests in A-study AD subjects and also B-study AD subjects for both co-primary variables (ADAS-cog and CDR-sb) have $p < 0.05$, (i.e., $p < 0.05$ for ADAS-cog demonstrating statistical superiority of azeliragon 5 mg added to SoC versus placebo added to SoC and also $p < 0.05$ for CDR-sb demonstrating statistical superiority of azeliragon 5 mg added to SoC versus placebo added to SoC, i.e., statistical significance of the test of the null hypothesis for each A-study and B-study independently), testing will proceed to the fifth set of

hypotheses to the expansion of the more heterogeneous population of AD subjects participating in the study, including all study subjects.

Consistent with the FDA draft Guidance for Industry: *Alzheimer's Disease: Developing Drugs for the Treatment of Early Stage Disease* (February, 2012), toward the goal of demonstrating disease modification, analysis of MRI data (selection and specification will be made prior to database lock) will be done conditional on significance of the above named hypothesis tests:

The next set of hypotheses to be tested is as follows:

- $H_{05}: \mu^{(MRI, \text{azeliragon, All})} = \mu^{(MRI, P, All)}$
- $H_{15}: \mu^{(MRI, \text{azeliragon, All})} \neq \mu^{(MRI, P, All)}$

where $\mu^{(MRI, \text{azeliragon, All})}$ and $\mu^{(MRI, P, All)}$ denote the true mean changes from Baseline at Month 18 on MRI volume measures for all AD azeliragon 5 mg/day and placebo groups, respectively.

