9.5.2 Statistical Methodology for Primary Analysis

The primary analysis will use the ITT methodology and a main-effects mixed-models for repeated measures (MMRM) methodology. The MMRM will utilize an unstructured covariance where the number of parameters is $t(t+1)/2$ where t is the dimension of the covariance matrix, using PROC MIXED in SAS. In the unlikely event of lack of convergence, Toeplitz structure will be employed where the number of parameters is t where t is the dimension of the covariance matrix. Time is considered as a class variable. Analysis will include treatment, time and treatment-by-time interaction as fixed effects, Baseline as covariate, baseline stratum as a covariate, and subject as a random effect. Supportive modeling will also include MMRM main-effects model with treatment, time, and subject.

The primary analysis will be done for each sub-study separately and will use $\alpha = 0.049$, which includes an adjustment of 0.001 for interim analyses performed by the Independent Data Monitoring Committee (IDMC), thereby preserving the overall study-wise $\alpha = 0.05$.

The primary analysis will also be done on randomization stratification subgroups defined by (1) baseline ADAS-cog 19 or less and (2) baseline ADAS-cog more than 19.

Multiple imputations (MI) will be used as a supportive analysis with 100 invocations (acknowledging that more invocations are needed with more missing data). Monte Carlo methods are planned.

An essential component of the thorough analysis includes an assessment of the impact of missing data on study conclusions. As a part of assessing this impact, supportive analysis will include an endpoint analysis (reduction to last-observation-carried-forward, justified in this study based on the monotonic progression of the natural course of AD and assuming no more dropouts in the group treated with azeliragon plus SoC than in the group treated with placebo plus SoC), a completers analysis (observed cases at Month 18), and observed cases by assessment time.

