## 1.9 Modifications from the Statistical Section of the Protocol

One modification from the Statistical Section of the Protocol is reflected in this SAP, based on agreement with the Neurology Products Division of the FDA:

- (1) Elimination of the use of Bazett's correction for QT-interval analysis, based on the recommendation depicted in ICH E14 Q&A R3 (dated 10 December 2015).

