## 5 Statistical Methodology

General statistical methods will be applied as appropriate for out-patient clinical studies. Safety evaluations will rely on descriptive statistics. Randomization groups will be examined for homogeneity between treatment groups.

Continuous variables will be summarized using mean, median, standard deviation, minimum, maximum, and number of subjects available for analysis. Categorical variables will be summarized using frequency, proportion, and number of subjects available for analysis.

The primary analysis is completely specified in the protocol, and that analysis is the intended analysis to be advanced as primary. Additionally, supportive analyses, sensitivity analyses, and secondary analyses will be done with respect to the primary endpoint.

SAS version 9.3 or later will be used.

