#### **5.2.1/5 Adjustments for multiplicity**

Multiplicity of the primary efficacy analyses is controlled by using a conditional sequence of hypotheses. The study will be considered to demonstrate statistical significance if the primary analysis has a resulting p-value less than 0.049 for both primary endpoints for both A-study and B-study. No other adjustment for multiplicity is required.

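### Do protocol 9.5.5 and SAP 5.2.1/5 leave it open whether the study succeeds when only one of A-study and B-study is positive?

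*Protocol*

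**What the plan says.** Protocol 9.5.5: "The study will be considered to demonstrate statistical significance if the primary analysis has a resulting p-value less than 0.05". The sentence before it says that multiplicity is controlled by the conditional sequence of hypotheses.

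SAP 5.2.1/5 repeats the sentence with a fuller condition: the study is significant if the primary analysis "has a resulting p-value less than 0.049 for both primary endpoints for both A-study and B-study".

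The other passages that bear on the rule are these.

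- Protocol 9.5.1.1 places change in ADAS-cog and change in CDR-sb together in the primary analysis.
- Protocol 9.5.2: "The primary analysis will be done for each sub-study separately and will use" an alpha of 0.049, the 0.001 being set aside for the data monitoring committee's looks.
- Protocol 9.2: "Stage 1: 4 concurrent analyses will be done", that is, two endpoints in each of two sub-studies. A note there says that 0.05 stands for whatever alpha is allocated. Stage 2 opens on this condition: "If and only if both hypothesis tests in A-study AD subjects and also B-study AD subjects for both co-primary variables" are significant.
- Protocol 9.0: "The SAP will supersede the protocol".
- SAP 1.9: "One modification from the Statistical Section of the Protocol is reflected in this SAP". The one item is dropping Bazett's correction.
- SAP 5: "The primary analysis is completely specified in the protocol, and that analysis is the intended analysis to be advanced as primary".

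**The concern.** Read alone, protocol 9.5.5 leaves the scope of the rule blank. Protocol 9.5.2 runs the primary analysis once per sub-study, so a p-value from the primary analysis could be taken to mean one sub-study's p-value. The requirement that all four tests succeed appears in the protocol only as the gate to the MRI test, not as the definition of success. The SAP supplies the missing scope but does not record having done so, and SAP 5 points back to the protocol for the primary analysis.

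If the rule were really open, two things would be at stake. A split is a realistic outcome even when the planned effects are true, so the conclusion could be chosen after the results are known. Error control would also depend on the choice. The four Stage 1 tests run side by side, so the conditional sequence does not protect them from one another; only the requirement that all four succeed does.

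**Working it through.** **1. The threshold.** Protocol 9.13 gives 0.0001 to each of at most 10 committee analyses: 0.05 − 10 × 0.0001 = 0.049. This reproduces the alpha in protocol 9.5.2 and SAP 5.2.1/5, so 0.049 is not new in the SAP.

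**2. The stated power** (protocol 9.1; two-sided two-sample t-test, noncentrality = difference ÷ (SD × √(2/n))).

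- ADAS-cog: 3.5 ÷ (9 × √(2/141)) = 3.27. Power is 90.2% at 0.05 and 90.1% at 0.049.
- CDR-sb: 0.9 ÷ (2.4 × √(2/152)) = 3.27. Power is 90.3% at 0.05 and 90.1% at 0.049.

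Both stated figures of at least 90% hold at either alpha. For all four tests together, moving from 0.05 to 0.049 costs between 0.16 points (200 per arm, correlation 0.9) and 0.39 points (160 per arm, correlation 0).

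**3. What the documents say about each outcome.**

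| Outcome | SAP 5.2.1/5 | Protocol 9.2 | Protocol 9.5.5 alone |
|---|---|---|---|
| Both sub-studies positive on both co-primaries | Success | Stage 2 opens | Success |
| Exactly one sub-study positive on both | Not success | Stage 2 closed | Unclear |
| Neither positive on both | Not success | Stage 2 closed | Unclear only if one endpoint were thought enough, which 9.5.1.1 excludes |

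The only unclear column is 9.5.5 read by itself. Protocol 9.0 resolves it in favour of the SAP column, and the protocol's own testing sequence agrees with that column.

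**4. How likely is a split?** Take 400 randomised per sub-study and 20% dropout, the plan's ceiling: 200 × 0.8 = 160 per arm. At alpha 0.049 the single-test powers are 0.9331 (ADAS-cog) and 0.9155 (CDR-sb). The documents give no correlation between the endpoints, so 0 to 0.9 is assumed. Let J be the probability that one sub-study passes both. The sub-studies are independent, so all four pass with probability J² and exactly one sub-study passes with probability 2J(1 − J).

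- Correlation 0: J = 0.9331 × 0.9155 = 0.854; J² = 73.0%; split = 24.9%.
- Correlation 0.9: J = 89.8%; J² = 80.7%; split = 18.3%.
- No dropout (200 per arm): split 12.2% to 8.9% over the same correlations.
- Phase 2 mild-subgroup differences (4.0 and 1, protocol 1.1.3) with the same SDs, 160 per arm: split 11.7% to 8.7%.

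**5. Error rates.** Suppose one co-primary truly works and the other is null in both sub-studies. If either sub-study sufficed, a false declaration could reach 1 − (1 − 0.049)² = 9.6% two-sided, or 1 − (1 − 0.0245)² = 4.8% in the favourable direction. Under the SAP rule it is at most 0.049² = 0.24%. If only one of the four hypotheses is null, the SAP rule still bounds the error at 0.049. The 9.6% belongs to a rule that neither document states.

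**The case for a change.** The best case for acting is about traceability. SAP 1.9 claims a single change, SAP 5 says the protocol fully specifies the primary analysis, and the protocol's use of the word study is elastic: in 9.1 it refers to the 354 patients who make up one sub-study. Someone defending a claim from a single sub-study could cite all three. Protocol 11.1 adds that each sub-study is locked, unblinded and reported as it completes, so A-study might be read before B-study.

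Part of this stands. Protocol 9.5.5 is loosely worded, its 0.05 does not match the 0.049 in 9.5.2, SAP 1.9 does not mention the explicit four-test wording, and neither document says how one positive sub-study would be described in a report.

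The rest does not reach the success rule. Precedence under protocol 9.0 does not depend on a change being listed in SAP 1.9. That list is incomplete anyway: it also omits the Stage 3 hierarchy and the revised per-protocol definition. The sentence in SAP 5 introduces the methodology and is most naturally read as covering the model and population rather than the decision rule. SAP 2 presents its testing sequence as the protocol's own. Protocol 11.1 deals with locking and reporting, and it also ties the lock to all participants having completed; reporting one sub-study is not declaring the study a success.

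**Conclusion.** The concern does not hold as a fault in the plan. An analyst following the documents reaches one conclusion for a split: no study-level significance and no Stage 2 or Stage 3 testing. That is also the conclusion that keeps the error rate at or below 0.049. Clearer wording in protocol 9.5.5 would alter no test, alpha, sample size or result.

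The split probability of about 9% to 25% is a property of asking for replication in two sub-studies, not of the wording. It rests on the planned effects and SDs, a t-test on completers, dropout from 0 to 20% and the assumed correlation of 0 to 0.9; the planned MMRM may do somewhat better. The reading of the success rule rests on none of these assumptions, only on protocol 9.0 and SAP 5.2.1/5. The mismatch between the two texts is a clerical slip that can be tidied whenever the documents are next revised.

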9.6 SAFETY ANALYSIS

The SAF is used for safety analysis. Adverse events, ECGs, vital signs and safety laboratory data will be reviewed and summarized on an ongoing basis during the trial to evaluate the safety of participants.

9.6.1 Safety Variables of Analysis

9.6.1.1 Adverse Events

Definitions:

- A *treatment-emergent adverse event* (TEAE) is an event that is observed or reported after administration of study medication that was not present prior to study medication administration or an event that represents the exacerbation of a pre-existing event.
- An *adverse withdrawal* is a subject who withdrew from the study due to an adverse event.
- A *serious adverse event* (SAE) is an AE that is classified as serious according to the criteria specified in the study protocol.

Adverse events variables of analysis include:

- Proportions of subjects with TEAEs by Preferred Term and decreasing frequency of TEAE
- Proportions of subjects with TEAEs by System Organ Class and Preferred Term
- Proportions of subjects with adverse withdrawals

9.6.1.2 Vital Signs

Vital signs measures of blood pressure and pulse will include the following variables of analysis:

- Mean values and mean changes of values from Baseline to Visit

- Proportions of subjects with clinically significant abnormal values or changes in vital signs measures.
- Proportions of subjects with AEs related to vital signs

9.6.1.3 Clinical Laboratory

Clinical Laboratory hematology and clinical chemistry variables of analysis include:

- Proportions of subjects with TEAVs (shifts from normal status to abnormal status)
- Proportions of subjects meeting DILI criteria per FDA guidance *Guidance for Industry “Drug-induced liver injury: premarketing clinical evaluation”* (CDER, CBER, July 2009)
- Means and mean changes from Baseline to Visit
- Proportions of subjects with new (post Baseline) clinically significant values (Clinical laboratory-related AEs) or changes in laboratory values

